10.5. Appendix 5: Contraceptive and Barrier Guidance and Collection of Pregnancy Information

Participants must follow contraceptive measures as outlined in Section 5.1, Inclusion Criteria. Pregnancy information will be collected and reported as noted in Section 8.3.4, Pregnancy, and Appendix 4: Adverse Events: Definitions and Procedures for Recording, Evaluating, Follow-up, and Reporting.

Definitions

Woman of Childbearing Potential (WOCBP)

A woman is considered fertile following menarche and until becoming postmenopausal unless permanently sterile (see below).

Woman Not of Childbearing Potential

premenarchal

A premenarchal state is one in which menarche has not yet occurred.

• postmenopausal

A postmenopausal state is defined as no menses for 12 months without an alternative medical cause. A high follicle stimulating hormone (FSH) level (>40 IU/L or mIU/mL) in the postmenopausal range may be used to confirm a postmenopausal state in female participants not using hormonal contraception or hormonal replacement therapy (HRT), however in the absence of 12 months of amenorrhea, a single FSH measurement is insufficient.

• permanently sterile

Permanent sterilization methods include hysterectomy, bilateral salpingectomy, bilateral tubal occlusion/ligation procedures, and bilateral oophorectomy.

Note: If the childbearing potential changes after start of the study (eg, a premenarchal female participant experiences menarche) or the risk of pregnancy changes (eg, a female participant who is not heterosexually active becomes active), a female participant must begin a highly effective method of contraception, as described throughout the inclusion criteria. If reproductive status is questionable, additional evaluation should be considered.

Contraceptive (birth control) use by male or female participants should be consistent with local regulations regarding the acceptable methods of contraception for those participating in clinical studies.

Typical use failure rates may differ from those when used consistently and correctly. Use should be consistent with local regulations regarding the use of contraceptive methods for participants in clinical studies.

Examples of Contraceptives

EXAMPLES OF CONTRACEPTIVES^a ALLOWED DURING THE STUDY INCLUDE:

USER INDEPENDENT

Highly Effective Methods That Are User Independent *Failure rate of* \leq 1% *per year when used consistently and correctly.*

- Implantable progestogen-only hormone contraception associated with inhibition of ovulation^b
- Intrauterine device (IUD)
- Intrauterine hormone-releasing system (IUS)
- Bilateral tubal occlusion
- Vasectomized partner

(Vasectomized partner is a highly effective contraceptive method provided that the partner is the sole sexual partner of the woman of childbearing potential and the absence of sperm has been confirmed. If not, additional highly effective method of contraception should be used. Spermatogenesis cycle is approximately 74 days.)

USER DEPENDENT

Highly Effective Methods That Are User Dependent *Failure rate of* <1% *per year when used consistently and correctly.*

- Estrogen-based hormonal contraception may not be reliable when taking the study drug. Therefore, to be eligible for this study, women of childbearing potential should either use:
 - a double-barrier method (male condom + either diaphragm or cervical cap); OR
 - non-estrogen hormonal based contraceptives in combination with a barrier contraceptive (male condom, diaphragm or cervical cap, or female condom); OR
 - intrauterine device in combination with a barrier contraceptive (male condom, diaphragm or cervical cap, or female condom).

Note: A male condom and female condom should not be used together due to risk of breakage or damage caused by latex friction.

- Progestogen-only hormone contraception associated with inhibition of ovulation^b
 - -oral
 - -injectable
- Sexual abstinence

(Sexual abstinence is considered a highly effective method only if defined as refraining from heterosexual intercourse during the entire period of risk associated with the study intervention. The reliability of sexual abstinence needs to be evaluated in relation to the duration of the study and the preferred and usual lifestyle of the participant.)

NOT ALLOWED AS SOLE METHOD OF CONTRACEPTION DURING THE STUDY (not considered to be highly effective - failure rate of >1% per year)

[figure not shown]
- Progestogen-only oral hormonal contraception where inhibition of ovulation is not the primary mode of action.
- Male or female condom with or without spermicide^c
- Cap, diaphragm, or sponge with spermicide
- A combination of male condom with either cap, diaphragm, or sponge with spermicide (double-barrier methods)^c
- Periodic abstinence (calendar, symptothermal, postovulation methods)
- Withdrawal (coitus-interruptus)
- Spermicides alone
- Lactational amenorrhea method (LAM)
- a) Typical use failure rates may differ from those when used consistently and correctly. Use should be consistent with local regulations regarding the use of contraceptive methods for participants in clinical studies.

TMC114+JNJ-48763364-AAA+JNJ-35807551-AAA+JNJ-63625328-ZCA (darunavir 800 mg/cobicistat 150 mg/emtricitabine 200 mg/tenofovir alafenamide 10 mg)

Clinical Protocol TMC114FD2HTX4004 Amendment 3

- b) Hormonal contraception may be susceptible to interaction with the study intervention, which may reduce the efficacy of the contraceptive method. In addition, consider if the hormonal contraception may interact with the study intervention.
- c) Male condom and female condom should not be used together (due to risk of failure with friction).

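### Protocol Appendix 5 classes condom plus diaphragm or cap both as a highly effective option for eligibility (<1% per year) and as not allowed on its own (>1% per year)

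*Protocol*

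**What the plan says.** Inclusion criterion 13 (Protocol Section 5.1) requires a woman of childbearing potential to use a method with a failure rate below 1% per year under consistent and correct use. It refers to Appendix 5 for examples. Appendix 5 in turn opens by referring back to Section 5.1.

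In Appendix 5, the heading for highly effective user-dependent methods carries the same limit of below 1% per year. Its first entry begins with a warning: "Estrogen-based hormonal contraception may not be reliable when taking the study drug". It continues: "Therefore, to be eligible for this study, women of childbearing potential should either use" one of three alternatives, the first being "a double-barrier method (male condom + either diaphragm or cervical cap); OR". The second is a non-estrogen hormonal method plus a barrier. The third is "intrauterine device in combination with a barrier contraceptive (male condom, diaphragm or cervical cap, or female condom".

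The following list is headed "NOT ALLOWED AS SOLE METHOD OF CONTRACEPTION DURING THE STUDY (not considered to be highly effective - failure rate of >1% per year". One of its entries is "A combination of male condom with either cap, diaphragm, or sponge with spermicide (double-barrier methods".

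Two kinds of method also appear both alone and with a required barrier. "Intrauterine device (IUD" stands by itself among the user-independent methods. Implantable, injectable and ovulation-inhibiting oral progestogen-only methods are also listed by themselves, with a footnote: "Hormonal contraception may be susceptible to interaction with the study intervention, which may reduce the efficacy of the contraceptive method".

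**The concern.** Criterion 13 sets a numerical threshold but names no methods, so Appendix 5 is where a site learns what qualifies. If one method falls on both sides of the threshold there, the criterion cannot be applied consistently to a woman who uses it. One site could enrol her on the strength of the eligibility bullet, and another could refuse her on the strength of the next list.

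At stake are the correctness of an eligibility rule and the pregnancy safeguard it serves. Section 5 of the protocol rules out waivers. If the stricter classification is the right one, enrolment under the bullet would be an eligibility deviation. Section 5 also tells investigators to consult the sponsor when a criterion is in question, but a site that reads only the eligibility bullet would see nothing to ask about.

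**Working it through.** The plan states no figure to reproduce here, so the check is a comparison of text, all from the current protocol.

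1. **The method is the same in both lists.** The eligibility bullet combines a male condom with a diaphragm or cervical cap. The not-allowed entry combines a male condom with a cap, diaphragm or sponge. Both use the term double barrier.

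2. **The classes exclude each other.** The first heading states a failure rate below 1% per year and the second a rate above 1% per year. A single method cannot have both, and criterion 13 accepts only the first.

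3. **The bullet offers a complete option.** The three alternatives are joined by either and or. The second and third spell out the barrier that must be added. The first names nothing further, so as written it is sufficient alone, which is the use the next list forbids.

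4. **Spermicide does not separate the entries.** The word appears only in the not-allowed entry. Treating the entries as different methods would mean that adding spermicide turns an acceptable method into an unacceptable one. The entry's own label is also general.

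5. **The estrogen lead-in does not separate them either.** Suppose the sentence is meant only for women who would otherwise use estrogen. Double barrier is still a complete alternative for those women under a heading of below 1%.

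6. **The cross-references do not settle it.** Section 5.1 points to Appendix 5 and Appendix 5 points to Section 5.1. Neither says elsewhere which class double barrier belongs to.

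7. **Number affected.** The cap of approximately 70% male participants (Section 4.1) implies roughly 0.30 × 110 = 33 or more women at the planned size. At the maximum after sample size re-estimation (Section 9.2) it implies 0.30 × 150 = 45 or more. These counts cover all women. The protocol does not say how many would be of childbearing potential or would rely on double barrier alone, so the range remains none to all enrolled women of childbearing potential.

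**The case against.** The best reconciling argument uses inclusion criterion 12. That criterion asks women on oral contraceptives to use an additional method beyond the one criterion 13 requires. The Appendix 5 bullet begins with estrogen-based contraception. If an estrogen user adds double barrier, it is not her only method and the not-allowed list is not breached. But the appendix does not say that double barrier is an addition, and the three alternatives read more naturally as replacements. Criterion 12 also presupposes that criterion 13 is already met by something else, so it cannot make double barrier qualify under criterion 13.

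A second objection is that the sponsor may have kept the eligibility sentence on purpose as study-specific text. That is possible and the documents do not exclude it. It would not make the two lists consistent, because the sponsor would still have to change one of them.

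The third objection is that the consequences are limited, and it stands. Pregnancy is tested in serum at screening and in urine at baseline and at the scheduled visits through Week 48 (Section 1.3). A participant who becomes pregnant is withdrawn (Section 8.3.4). Section 2.2 reports no significant adverse effects in developmental toxicity studies of the four components.

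A reader might also infer some stronger points that the documents do not support:

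- The eligibility sentence does not restrict every woman of childbearing potential to the three alternatives. The same page accepts tubal occlusion, a vasectomized partner and abstinence.
- The double listing of the IUD and the progestogen-only methods is not a second breach of criterion 13. Each is listed alone as highly effective, and adding a barrier is only stricter. It is an ambiguity to clear up.
- Nothing shows that only a few women, or indeed any, relied on double barrier alone.

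**Conclusion.** The eligibility bullet is wrong as written. It presents as highly effective, and sufficient for eligibility, a method that the same appendix classes as not highly effective and not acceptable alone. A site could follow the bullet in good faith and enrol a woman who does not meet criterion 13.

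Calling such an enrolment a deviation assumes that the not-allowed classification is the intended one. That is the conservative assumption and the one under which the appendix agrees with criterion 13, but the documents do not confirm it. The contradiction itself does not depend on that assumption.

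The severity is minor. The primary endpoint, its analysis, the power and the type I error are unaffected, and the existing pregnancy monitoring limits the harm.

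**What to change.** Remove double barrier as a stand-alone alternative from the eligibility bullet in Appendix 5, or state there that it may be used only in addition to a highly effective method. Either wording brings the bullet into line with criterion 13 and with the not-allowed list.

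In the same edit, state whether an IUD and the implantable, injectable and oral progestogen-only methods need an added barrier.

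The cost is one change to the appendix text and a clarification to sites. Any woman who relies on double barrier alone would need another method. Data collection and analysis do not change.

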10.6. Appendix 6: Management of Clinically Significant Laboratory Toxicities

^a Mandatory confirmation is not warranted for asymptomatic Grade 3 or Grade 4 glucose elevations in participants with pre-existing diabetes, and asymptomatic Grade 3 or Grade 4 triglyceride or cholesterol elevations.

104

10.7. Appendix 7: DAIDS Table for Grading the Severity of Adult and Pediatric Adverse Events

The Division of AIDS Table for Grading the Severity of Adult and Pediatric Adverse Events (v 2.1, July 2017), or 'DAIDS grading table', is a descriptive terminology to be utilized for adverse event reporting in this study. A grading (severity) scale is provided for each adverse event term.

General Considerations

The Division of AIDS (DAIDS) Table for Grading the Severity of Adult and Pediatric Adverse Events, Version 2.1 consists of parameters, or AEs, with severity grading guidance that are to be used in DAIDS clinical trials for safety data reporting to maintain accuracy and consistency in the evaluation of AEs. The term "severe" is not the same as the term "serious" in classifying AEs. The severity of a specific event describes its intensity, and it is the intensity which is graded. Seriousness, which is not graded, relates to an outcome of an AE and is a regulatory definition.

Clinical sites are encouraged to report parameters in the DAIDS grading table as they are written to maintain data consistency across clinical trials. However, since some parameters can be reported with more specificity, clinical sites are encouraged to report parameters that convey additional clinical information. For example, diarrhea could be reported as neonatal diarrhea; seizures, as febrile seizures; and pain, as jaw pain.

The DAIDS grading table provides an AE severity grading scale ranging from grades 1 to 5 with descriptions for each AE based on the following general guidelines:

- Grade 1 indicates a mild event
- Grade 2 indicates a moderate event
- Grade 3 indicates a severe event
- Grade 4 indicates a potentially life-threatening event
- Grade 5 indicates death (*Note*: This grade is not specifically listed on each page of the grading table).

Other points to consider include:

- Use age and sex values as applicable.
- Unless noted, laboratory values are for term neonates. Preterm neonates should be assessed using local laboratory normal ranges.
- Where applicable, Standard International (SI) units are included in italics.

Selecting and Reporting a Primary AE Term

When selecting a primary AE term to report, sites should select the term that best describes what

occurred to the participant. For example, a participant may present with itching, urticaria, flushing, angioedema of the face, and dyspnea. If the underlying diagnosis is determined to be an acute allergic reaction, sites should report "Acute Allergic Reaction" as the primary AE term.

Determining Severity Grade for Parameters between Grades

If the severity of an AE could fall in either one of two grades (i.e., the severity of an AE could be either grade 2 or grade 3), sites should select the higher of the two grades.

Estimating Severity Grade for Parameters Not Identified in the Grading Table

The functional table below should be used to grade the severity of an AE that is not specifically identified in the grading table. In addition, all deaths related to an AE are to be classified as grade 5.

PARAMETER	GRADE 1 MILD	GRADE 2 MODERATE	GRADE 3 SEVERE	GRADE 4 POTENTIALLY LIFE- THREATENING
Clinical adverse event NOT identified elsewhere in the grading table	Mild symptoms causing no or minimal interference with usual social & functional activities with intervention not indicated	Moderate symptoms causing greater than minimal interference with usual social & functional activities with intervention indicated	Severe symptoms causing inability to perform usual social & functional activities with intervention or hospitalization indicated	Potentially life threatening symptoms causing inability to perform basic self care functions with intervention indicated to prevent permanent impairment, persistent disability, or death

Major Clinical Conditions Cardiovascular

PARAMETER	GRADE 1 MILD	GRADE 2 MODERATE	GRADE 3 SEVERE	GRADE 4 POTENTIALLY LIFE- THREATENING	
Arrhythmia (by ECG or physical examination) Specify type, if applicable	No symptoms AND No intervention indicated	No symptoms AND Non urgent intervention indicated	Non life threatening symptoms AND Non urgent intervention indicated	Life threatening arrhythmia OR Urgent intervention indicated	
Blood Pressure Abnormalities¹ Hypertension (with the lowest reading taken after repeat testing during a visit) ≥ 18 years of age	140 to < 160 mmHg systolic OR 90 to < 100 mmHg diastolic	≥ 160 to < 180 mmHg systolic OR ≥ 100 to < 110 mmHg diastolic	≥ 180 mmHg systolic OR ≥ 110 mmHg diastolic	Life threatening consequences in a participant not previously diagnosed with hypertension (e.g., malignant hypertension) OR Hospitalization indicated	
< 18 years of age	> 120/80 mmHg	≥ 95 th to < 99 th percentile + 5 mmHg adjusted for age, height, and gender (systolic and/or diastolic)	≥ 99th percentile + 5 mmHg adjusted for age, height, and gender (systolic and/or diastolic)	Life threatening consequences in a participant not previously diagnosed with hypertension (e.g., malignant hypertension) OR Hospitalization indicated	
Hypotension	No symptoms	Symptoms corrected with oral fluid replacement	Symptoms AND IV fluids indicated	Shock requiring use of vasopressors or mechanical assistance to maintain blood pressure	
Cardiac Ischemia or Infarction Report only one	NA	NA	New symptoms with ischemia (stable angina) OR New testing consistent with ischemia	Unstable angina OR Acute myocardial infarction	
Heart Failure	No symptoms AND Laboratory or cardiac imaging abnormalities	Symptoms with mild to moderate activity or exertion	Symptoms at rest or with minimal activity or exertion (e.g., hypoxemia) OR Intervention indicated (e.g., oxygen)	Life threatening consequences OR Urgent intervention indicated (e.g., vasoactive medications, ventricular assist device, heart transplant)	

Blood pressure norms for children < 18 years of age can be found in: Expert Panel on Integrated Guidelines for Cardiovascular Health and Risk Reduction in Children and Adolescents. *Pediatrics* 2011;128;S213; originally published online November 14, 2011; DOI: 10.1542/peds.2009 2107C.

DAIDS AE Grading Table Corrected Version 2.1-July 2017 Page 31

Cardiovascular

PARAMETER	GRADE 1 MILD	GRADE 2 MODERATE	GRADE 3 SEVERE	GRADE 4 POTENTIALLY LIFE- THREATENING
Hemorrhage (with significant acute blood loss)	NA	Symptoms AND No transfusion indicated	Symptoms AND Transfusion of ≤ 2 units packed RBCs indicated	Life threatening hypotension OR Transfusion of > 2 units packed RBCs (for children, packed RBCs > 10 cc/kg) indicated
Prolonged PR Interval or AV Block Report only one > 16 years of age	PR interval 0.21 to < 0.25 seconds	PR interval ≥ 0.25 seconds OR Type I 2 nd degree AV block	Type II 2 nd degree AV block OR Ventricular pause ≥ 3.0 seconds	Complete AV block
≤ 16 years of age	1st degree AV block (PR interval > normal for age and rate)	Type I 2 nd degree AV block	Type II 2 nd degree AV block OR Ventricular pause ≥ 3.0 seconds	Complete AV block
Prolonged QTc Interval ²	0.45 to 0.47 seconds	> 0.47 to 0.50 seconds	> 0.50 seconds OR ≥ 0.06 seconds above baseline	Life threatening consequences (e.g., Torsade de pointes, other associated serious ventricular dysrhythmia)
Thrombosis or Embolism Report only one	NA	Symptoms AND No intervention indicated	Symptoms AND Intervention indicated	Life threatening embolic event (e.g., pulmonary embolism, thrombus)

As per Bazett's formula.

Dermatologic

PARAMETER	GRADE 1 MILD	GRADE 2 MODERATE	GRADE 3 SEVERE	GRADE 4 POTENTIALLY LIFE- THREATENING
Alopecia (scalp only)	Detectable by study participant, caregiver, or physician AND Causing no or minimal interference with usual social & functional activities	Obvious on visual inspection AND Causing greater than minimal interference with usual social & functional activities	NA	NA
Bruising	Localized to one area	Localized to more than one area	Generalized	NA
Cellulitis	NA	Non parenteral treatment indicated (e.g., oral antibiotics, antifungals, antivirals)	IV treatment indicated (e.g., IV antibiotics, antifungals, antivirals)	Life threatening consequences (e.g., sepsis, tissue necrosis)
Hyperpigmentation	Slight or localized causing no or minimal interference with usual social & functional activities	Marked or generalized causing greater than minimal interference with usual social & functional activities	NA	NA
Hypopigmentation	Slight or localized causing no or minimal interference with usual social & functional activities	Marked or generalized causing greater than minimal interference with usual social & functional activities	NA	NA
Petechiae	Localized to one area	Localized to more than one area	Generalized	NA
Pruritus ³ (without skin lesions)	Itching causing no or minimal interference with usual social & functional activities	Itching causing greater than minimal interference with usual social & functional activities	Itching causing inability to perform usual social & functional activities	NA

For pruritus associated with injections or infusions, see the Site Reactions to Injections and Infusions section (page 23).

DAIDS AE Grading Table Corrected Version 2.1 July 2017

Page 108

Rash Specify type, if applicable	Localized rash	Diffuse rash OR Target lesions	Diffuse rash AND Vesicles or limited number of bullae or superficial ulcerations of mucous membrane limited to one site	Extensive or generalized bullous lesions OR Ulceration of mucous membrane involving two or more distinct mucosal sites OR Stevens Johnson syndrome OR Toxic epidermal necrolysis
--	----------------	--	---	---

Endocrine and Metabolic

PARAMETER	GRADE 1 MILD	GRADE 2 MODERATE	GRADE 3 SEVERE	GRADE 4 POTENTIALLY LIFE- THREATENING
Diabetes Mellitus	Controlled without medication	Controlled with medication OR Modification of current medication regimen	Uncontrolled despite treatment modification OR Hospitalization for immediate glucose control indicated	Life threatening consequences (e.g., ketoacidosis, hyperosmolar non ketotic coma, end organ failure)
Gynecomastia	Detectable by study participant, caregiver, or physician AND Causing no or minimal interference with usual social & functional activities	Obvious on visual inspection AND Causing pain with greater than minimal interference with usual social & functional activities	Disfiguring changes AND Symptoms requiring intervention or causing inability to perform usual social & functional activities	NA
Hyperthyroidism	No symptoms AND Abnormal laboratory value	Symptoms causing greater than minimal interference with usual social & functional activities OR Thyroid suppression therapy indicated	Symptoms causing inability to perform usual social & functional activities OR Uncontrolled despite treatment modification	Life threatening consequences (e.g., thyroid storm)
Hypothyroidism	No symptoms AND Abnormal laboratory value	Symptoms causing greater than minimal interference with usual social & functional activities OR Thyroid replacement therapy indicated	Symptoms causing inability to perform usual social & functional activities OR Uncontrolled despite treatment modification	Life threatening consequences (e.g., myxedema coma)
Lipoatrophy ⁴	Detectable by study participant, caregiver, or physician AND Causing no or minimal interference with usual social & functional activities	Obvious on visual inspection AND Causing greater than minimal interference with usual social & functional activities	Disfiguring changes	NA

Definition: A disorder characterized by fat loss in the face, extremities, and buttocks.

DAIDS AE Grading Table Corrected Version 2.1 July 2017 Page 10

Endocrine and Metabolic

PARAMETER	GRADE 1 MILD	GRADE 2 MODERATE	GRADE 3 SEVERE	GRADE 4 POTENTIALLY LIFE- THREATENING
Lipohypertrophy ⁵	Detectable by study participant, caregiver, or physician AND Causing no or minimal interference with usual social & functional activities	Obvious on visual inspection AND Causing greater than minimal interference with usual social & functional activities	Disfiguring changes	NA

CONFIDENTIAL - FOIA Exemptions Apply in U.S.

Definition: A disorder characterized by abnormal fat accumulation on the back of the neck, breasts, and abdomen.

Gastrointestinal

PARAMETER	GRADE 1 MILD	GRADE 2 MODERATE	GRADE 3 SEVERE	GRADE 4 POTENTIALLY LIFE- THREATENING
Anorexia	Loss of appetite without decreased oral intake	Loss of appetite associated with decreased oral intake without significant weight loss	Loss of appetite associated with significant weight loss	Life threatening consequences OR Aggressive intervention indicated (e.g., tube feeding, total parenteral nutrition)
Ascites	No symptoms	Symptoms AND Intervention indicated (e.g., diuretics, therapeutic paracentesis)	Symptoms recur or persist despite intervention	Life threatening consequences
Bloating or Distension Report only one	Symptoms causing no or minimal interference with usual social & functional activities	Symptoms causing greater than minimal interference with usual social & functional activities	Symptoms causing inability to perform usual social & functional activities	NA
Cholecystitis	NA	Symptoms AND Medical intervention indicated	Radiologic, endoscopic, or operative intervention indicated	Life threatening consequences (e.g., sepsis, perforation)
Constipation	NA	Persistent constipation requiring regular use of dietary modifications, laxatives, or enemas	Obstipation with manual evacuation indicated	Life threatening consequences (e.g., obstruction)
Diarrhea ≥ 1 year of age	Transient or intermittent episodes of unformed stools OR Increase of ≤ 3 stools over baseline per 24 hour period	Persistent episodes of unformed to watery stools OR Increase of 4 to 6 stools over baseline per 24 hour period	Increase of ≥ 7 stools per 24 hour period OR IV fluid replacement indicated	Life threatening consequences (e.g., hypotensive shock)
< 1 year of age	Liquid stools (more unformed than usual) but usual number of stools	Liquid stools with increased number of stools OR Mild dehydration	Liquid stools with moderate dehydration	Life threatening consequences (e.g., liquid stools resulting in severe dehydration, hypotensive shock)
Dysphagia or Odynophagia Report only one and specify location	Symptoms but able to eat usual diet	Symptoms causing altered dietary intake with no intervention indicated	Symptoms causing severely altered dietary intake with intervention indicated	Life threatening reduction in oral intake
Gastrointestinal Bleeding	Not requiring intervention other than iron supplement	Endoscopic intervention indicated	Transfusion indicated	Life threatening consequences (e.g., hypotensive shock)

AIDS AE Grading Table Corrected Version 2.1 July 2017 Page 37

Gastrointestinal

PARAMETER	GRADE 1 MILD	GRADE 2 MODERATE	GRADE 3 SEVERE	GRADE 4 POTENTIALLY LIFE- THREATENING
Mucositis or Stomatitis Report only one and specify location	Mucosal erythema	Patchy pseudomembranes or ulcerations	Confluent pseudomembranes or ulcerations OR Mucosal bleeding with minor trauma	Life threatening consequences (e.g., aspiration, choking) OR Tissue necrosis OR Diffuse spontaneous mucosal bleeding
Nausea	Transient (< 24 hours) or intermittent AND No or minimal interference with oral intake	Persistent nausea resulting in decreased oral intake for 24 to 48 hours	Persistent nausea resulting in minimal oral intake for > 48 hours OR Rehydration indicated (e.g., IV fluids)	Life threatening consequences (e.g., hypotensive shock)
Pancreatitis	NA	Symptoms with hospitalization not indicated	Symptoms with hospitalization indicated	Life threatening consequences (e.g., circulatory failure, hemorrhage, sepsis)
Perforation (colon or rectum)	NA	NA	Intervention indicated	Life threatening consequences
Proctitis	Rectal discomfort with no intervention indicated	Symptoms causing greater than minimal interference with usual social & functional activities OR Medical intervention indicated	Symptoms causing inability to perform usual social & functional activities OR Operative intervention indicated	Life threatening consequences (e.g., perforation)
Rectal Discharge	Visible discharge	Discharge requiring the use of pads	NA	NA
Vomiting	Transient or intermittent AND No or minimal interference with oral intake	Frequent episodes with no or mild dehydration	Persistent vomiting resulting in orthostatic hypotension OR Aggressive rehydration indicated (e.g., IV fluids)	Life threatening consequences (e.g., hypotensive shock)

Musculoskeletal

PARAMETER	GRADE 1 MILD	GRADE 2 MODERATE	GRADE 3 SEVERE	GRADE 4 POTENTIALLY LIFE- THREATENING
Arthralgia	Joint pain causing no or minimal interference with usual social & functional activities	Joint pain causing greater than minimal interference with usual social & functional activities	Joint pain causing inability to perform usual social & functional activities	Disabling joint pain causing inability to perform basic self care functions
Arthritis	Stiffness or joint swelling causing no or minimal interference with usual social & functional activities	Stiffness or joint swelling causing greater than minimal interference with usual social & functional activities	Stiffness or joint swelling causing inability to perform usual social & functional activities	Disabling joint stiffness or swelling causing inability to perform basic self care functions
Myalgia (generalized)	Muscle pain causing no or minimal interference with usual social & functional activities	Muscle pain causing greater than minimal interference with usual social & functional activities	Muscle pain causing inability to perform usual social & functional activities	Disabling muscle pain causing inability to perform basic self care functions
Osteonecrosis	NA	No symptoms but with radiographic findings AND No operative intervention indicated	Bone pain with radiographic findings OR Operative intervention indicated	Disabling bone pain with radiographic findings causing inability to perform basic self care functions
Osteopenia ⁶ ≥ 30 years of age	BMD t score 2.5 to 1	NA	NA	NA
< 30 years of age	BMD z score 2 to 1	NA	NA	NA
Osteoporosis ⁶ ≥ 30 years of age	NA	BMD t score < 2.5	Pathologic fracture (e.g., compression fracture causing loss of vertebral height)	Pathologic fracture causing life threatening consequences
< 30 years of age	NA	BMD z score < 2	Pathologic fracture (e.g., compression fracture causing loss of vertebral height)	Pathologic fracture causing life threatening consequences

⁶ BMD t and z scores can be found in: Kan is JA on behalf of the World Health Organization Scientific Group (2007). Assessment of osteoporosis at the primary health care level. Technical Report. World Health Organization Collaborating Centre for

Metabolic Bone Diseases, University of Sheffield, UK. 2007: Printed by the University of Sheffield.

CONFIDENTIAL - FOIA Exemptions Apply in U.S.

Neurologic

PARAMETER	GRADE 1 MILD	GRADE 2 MODERATE	GRADE 3 SEVERE	GRADE 4 POTENTIALLY LIFE- THREATENING
Acute CNS Ischemia	NA	NA	Transient ischemic attack	Cerebral vascular accident (e.g., stroke with neurological deficit)
Altered Mental Status (for Dementia, see Cognitive, Behavioral, or Attentional Disturbance below)	Changes causing no or minimal interference with usual social & functional activities	Mild lethargy or somnolence causing greater than minimal interference with usual social & functional activities	Confusion, memory impairment, lethargy, or somnolence causing inability to perform usual social & functional activities	Delirium OR Obtundation OR Coma
Ataxia	Symptoms causing no or minimal interference with usual social & functional activities OR No symptoms with ataxia detected on examination	Symptoms causing greater than minimal interference with usual social & functional activities	Symptoms causing inability to perform usual social & functional activities	Disabling symptoms causing inability to perform basic self care functions
Cognitive, Behavioral, or Attentional Disturbance (includes dementia and attention deficit disorder) Specify type, if applicable	Disability causing no or minimal interference with usual social & functional activities OR Specialized resources not indicated	Disability causing greater than minimal interference with usual social & functional activities OR Specialized resources on part time basis indicated	Disability causing inability to perform usual social & functional activities OR Specialized resources on a full time basis indicated	Disability causing inability to perform basic self care functions OR Institutionalization indicated
Developmental Delay < 18 years of age Specify type, if applicable	Mild developmental delay, either motor or cognitive, as determined by comparison with a developmental screening tool appropriate for the setting	Moderate developmental delay, either motor or cognitive, as determined by comparison with a developmental screening tool appropriate for the setting	Severe developmental delay, either motor or cognitive, as determined by comparison with a developmental screening tool appropriate for the setting	Developmental regression, either motor or cognitive, as determined by comparison with a developmental screening tool appropriate for the setting
Headache	Symptoms causing no or minimal interference with usual social & functional activities	Symptoms causing greater than minimal interference with usual social & functional activities	Symptoms causing inability to perform usual social & functional activities	Symptoms causing inability to perform basic self care functions OR Hospitalization indicated OR Headache with significant impairment of alertness or other neurologic function

PARAMETER	GRADE 1 MILD	GRADE 2 MODERATE	GRADE 3 SEVERE	GRADE 4 POTENTIALLY LIFE- THREATENING
Neuromuscular Weakness (includes myopathy and neuropathy) Specify type, if applicable	Minimal muscle weakness causing no or minimal interference with usual social & functional activities OR No symptoms with decreased strength on examination	Muscle weakness causing greater than minimal interference with usual social & functional activities	Muscle weakness causing inability to perform usual social & functional activities	Disabling muscle weakness causing inability to perform basic self care functions OR Respiratory muscle weakness impairing ventilation
Neurosens ory Alteration (includes paresthesia and painful neuropathy) Specify type, if applicable	Minimal paresthesia causing no or minimal interference with usual social & functional activities OR No symptoms with sensory alteration on examination	Sensory alteration or paresthesia causing greater than minimal interference with usual social & functional activities	Sensory alteration or paresthesia causing inability to perform usual social & functional activities	Disabling sensory alteration or paresthesia causing inability to perform basic self care functions
Seizures New Onset Seizure ≥ 18 years of age	NA	NA	1 to 3 seizures	Prolonged and repetitive seizures (e.g., status epilepticus) OR Difficult to control (e.g., refractory epilepsy)
< 18 years of age (includes new or pre existing febrile seizures)	Seizure lasting < 5 minutes with < 24 hours postictal state	Seizure lasting 5 to < 20 minutes with < 24 hours postictal state	Seizure lasting ≥ 20 minutes OR > 24 hours postictal state	Prolonged and repetitive seizures (e.g., status epilepticus) OR Difficult to control (e.g., refractory epilepsy)
Pre existing Seizure	NA	Increased frequency from previous level of control without change in seizure character	Change in seizure character either in duration or quality (e.g., severity or focality)	Prolonged and repetitive seizures (e.g., status epilepticus) OR Difficult to control (e.g., refractory epilepsy)
Syncope	Near syncope without loss of consciousness (e.g., pre syncope)	Loss of consciousness with no intervention indicated	Loss of consciousness AND Hospitalization or intervention required	NA

Pregnancy, Puerperium, and Perinatal

PARAMETER	GRADE 1 MILD	GRADE 2 MODERATE	GRADE 3 SEVERE	GRADE 4 POTENTIALLY LIFE- THREATENING
Stillbirth (report using mother's participant ID) Report only one	NA	NA	Fetal death occurring at ≥ 20 weeks gestation	NA
Preterm Birth (report using mother's participant ID)	Live birth at 34 to < 37 weeks gestational age	Live birth at 28 to < 34 weeks gestational age	Live birth at 24 to < 28 weeks gestational age	Live birth at < 24 weeks gestational age
Spontaneous Abortion or Miscarriage ⁷ (report using mother's participant ID)	Chemical pregnancy	Uncomplicated spontaneous abortion or miscarriage	Complicated spontaneous abortion or miscarriage	NA
Report only one				

Definition: A pregnancy loss occurring at < 20 weeks gestational age.

Psychiatric

PARAMETER	GRADE 1 MILD	GRADE 2 MODERATE	GRADE 3 SEVERE	GRADE 4 POTENTIALLY LIFE- THREATENING
Ins omnia	Mild difficulty falling asleep, staying asleep, or waking up early causing no or minimal interference with usual social & functional activities	Moderate difficulty falling asleep, staying asleep, or waking up early causing more than minimal interference with usual social & functional activities	Severe difficulty falling asleep, staying asleep, or waking up early causing inability to perform usual social & functional activities requiring intervention or hospitalization	NA
